4.9 Primary Hypothesis and Study Endpoints

Primary Study Hypothesis

The CPAP Treatment group will have greater improvement on the SF-36 Energy and Vitality subscale score in patients with mild OSA **per AASM 2012 guidelines** compared to the Control group.

Primary Endpoint

Change in the Energy and Vitality Subscale Score of the SF 36 questionnaire from baseline (pre-treatment) to 3 months in mild OSA patients **per AASM 2012 guidelines**.

Secondary Endpoints

Change in outcome scores between baseline (pre-treatment) and 3 months in mild OSA patients **per AASM 2012 guidelines** in using the following quality of life measures:

SF-36 (7 subscales not previously assessed as the primary endpoint, PCS and MCS summary scores)
ESS
FSS total score
FOSQ total score
HADS Anxiety and Depression scores
ISI total score
Euroqol EQ-5D index
VAS score

Change in outcome scores between baseline (pre-treatment) and 3 months in mild OSA patients **per AASM 2007 guidelines** in the following quality of life measures:

SF-36 (8 subscales, PCS and MCS summary scores)
ESS

FSS total score
 FOSQ total score
 HADS Anxiety and Depression scores
 ISI total score
 Euroqol EQ-5D index
 VAS score

4.10 Outcomes Assessment Schedule

The following outcome measures will be assessed at baseline (before randomisation) and 3 months post treatment initiation.

Outcome	Baseline	3 days	3 months
Demographics & History	✓		
Home Sleep Test	✓		
Troubleshoot Phone Call		✓	
SF-36	✓		✓
ESS	✓		✓
FSS	✓		✓
FOSQ	✓		✓
HADS	✓		✓
ISI	✓		✓
Euroqol EQ-5D	✓		✓
CPAP Questionnaire			✓

5. STATISTICAL METHODS

5.1 Study Populations and Analysis Groups

There are two main study populations in this trial, one group fulfilling the mild OSA AASM 2012 guidelines and the second fulfilling the mild OSA AASM 2007 guidelines. Some trial patients will fulfil both criteria and will therefore be eligible for analysis under both AASM 2007 and AASM 2012. A third study population will consist of patients who fall into the category of Moderate to Severe OSA based on the AASM 2012 guidelines. Patients in this third population will either have tested as No OSA (AHI < 5 e/hr) or Mild OSA based on AASM 2007 guidelines.

The primary endpoint analysis will only be conducted on mild OSA patients per AASM 2012 guidelines. Each secondary endpoint analysis will be carried out on mild OSA patients based on AASM 2012 and AASM 2007 guidelines. Additionally, secondary analyses will be generated descriptively for the subgroup of patients with Moderate to Severe OSA per AASM 2012 guidelines. Therefore, all patients randomised into the trial will be analysed in one or more secondary analyses, with a subset of these patients fulfilling the AASM 2012 guidelines and qualifying for the primary analysis.

The intention to treat (ITT) analysis population will include all randomised patients. The ITT population will be further subdivided as follows:

ITT-1 population includes patients in the ITT with mild OSA per AASM 2012 guidelines.

ITT-2 population includes patients in the ITT with mild OSA per AASM 2007 guidelines.

ITT-3 population includes patients in the ITT with moderate to severe OSA per AASM 2012 guidelines.

The primary endpoint analysis, pool-ability analysis (see Section 5.3) and comparability of baseline characteristics will be generated for the ITT-1 population.

The completed cases (CC) analysis population will be a subset of the ITT population that includes patients who complete the 3-month study visit. [It is possible for there to be missing values for one or more outcome measures in the CC group, if a patient who completes the visits does not complete the questionnaires completely.] The CC population will be further subdivided as follows:

CC-1 population includes patients in the CC with mild OSA per AASM 2012 guidelines.

CC-2 population includes patients in the CC with mild OSA per AASM 2007 guidelines.

CC-3 population includes patients in the CC with moderate to severe OSA per AASM 2012 guidelines.

The secondary endpoint analyses will be generated for the CC-1, CC-2 and CC-3 populations, as specified.

5.2 Multiplicity

There is only one primary hypothesis in this study and therefore, no adjustments are required for multiple primary hypotheses.

5.3 Data Pooling

The issue of pool-ability of the data entails two features: the combining of data across study sites and the method of computation of an overall estimate for the primary study endpoint. The justification for combining of data across sites is based on the clinical assessment provided by Meinert (1986): the clinical study will be conducted under a common protocol for each investigational site, the study sites will be monitored for protocol compliance, and the same data gathering instruments and methods will be used in every site.

In order to test homogeneity of the primary endpoint across study sites and account for possible differences in demographic characteristics at study sites, a mixed-effects regression model for the ITT-1 population will be constructed with the change in the Energy and Vitality subscale of the SF-36 questionnaire from baseline (i.e., pre-treatment) to 3 months post-randomization as the dependent variable and will include site, treatment group and a site-by-treatment group interaction as a fixed effects. If the treatment-by-site interaction is statistically significant, this may imply that the treatment effect differs across study sites. The treatment-by-site interaction will be tested at a significance level of 0.10. If a treatment-by-site interaction is significant, a mixed-effects regression model with the following additional covariates will be considered to see if they help to explain the treatment-by-site interaction: baseline Energy and Vitality score, percentage adherent for the Treatment group at each site, and other baseline and demographic variables that are unbalanced across study sites.

In the case that there is a statistically significant treatment-by-site interaction, meaning that the treatment effect is heterogenous across study sites, then study site and treatment*site will be

included as random effects in the mixed-effects repeated measures model for the primary endpoint analysis.

The pool-ability analysis of study sites may require the formation of pseudo-sites because small sites will not provide appropriate information to allow the analysis above. The formation of pseudo-sites will be done without regard to effect size. Sites will be combined into pseudo-sites in an unbiased way, using the sorted study site numbers. Study sites with fewer than 6 patients will be combined in the following manner. The first site with less than 6 patients will be combined with the next site numbered in consecutive order with less than 6 patients. If this combination produces a size for the combined sites that is lower than the mean size for all study sites in the study, the next site will be added, as long as the total is less than or equal to the mean size for the study. If that site makes the size bigger than the mean size, the next site will be considered for inclusion in the pseudo-site. If no additional sites can be found that can be added and the size remain less than or equal to the mean of the study site sizes, that pseudo-site will be closed and another will be started with the first site that could not be added to the previous pseudo-site. This process continues until all small sites are combined into pseudo-sites. The remaining study sites with size of 6 or more patients will be assigned pseudo-site numbers. If there is but one site remaining with less than 6 patients, that site will be added to the smallest of the study sites that have at least 6 patients.

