4.2 Enrolment Target and Inclusion/Exclusion Criteria

The MERGE study is a prospective multicentre randomised parallel trial with 3 months of active treatment versus a control arm. Randomisation with minimisation will be performed with a 1:1 treatment group allocation.

Date of start of recruitment:	26 October 2016
Date of expected end of recruitment:	31 December 2018
Date expected end follow-up:	31 March 2019
Target number of subjects:	224 (112 per arm)
Participating Centres:	11

A patient will be eligible for inclusion in the study if all the following inclusion criteria apply:

- AHI 5-15 events/hr as per AASM 2007 scoring criteria or AHI ≥ 5 per AASM 2012 if AHI 0-4.9 per AASM 2007
- Aged ≥ 18 and ≤ 80 years
- Ability and willingness to provide written informed consent
- Ability to tolerate a CPAP one hour long run-in test

A patient will not be eligible for the study if any of the following exclusion criteria apply:

- The presence of unstable cardiac disease at trial screening
- Inability to give fully informed consent
- Use of supplemental oxygen
- Secondary sleep pathology e.g. Periodic Limb Movement Syndrome, Narcolepsy, Circadian Disorder, Obesity Hypoventilation Syndrome
- Epworth Sleepiness Scale (ESS) ≥ 15 , or concerns about sleepy driving from physician/ sleep lab staff
- Body Mass Index (BMI) $\geq 40 \text{ kg/m}^2$
- Previous CPAP usage

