4.6 Sample Size

The sample size of 224 (112 per arm) is based on statistics observed in the MOSAIC study: a mean score difference of 6.6 was observed between 3 months and baseline (considered a significant clinical improvement by the authors of the study) in the Energy and Vitality subscale of the SF-36 questionnaire, with a mean change of 4.2 (SD 18.1) in the Control group and 10.8 (SD 17.0) in the CPAP Treatment group. The sample size calculation is based on a two-sided 5% significance level and 80% power.

It is estimated that approximately 300 participants will need to be randomised in order to reach the required sample size of 224 patients with mild OSA **per AASM 2012 guidelines**. Subjects who are eligible for Home Sleep Testing (HST) are evaluated for their level of OSA. Those patients who have Mild OSA **per AASM 2007 guidelines** are eligible for randomisation. Those patients who have No OSA **per AASM 2007 guidelines** are further assessed based on the AASM 2012 guidelines. All patients with

AHI \geq 5 per AASM 2012 guidelines are also eligible for randomisation. Since the primary endpoint analysis is based on patients with mild OSA per AASM 2012 guidelines, there will be some patients randomised who will not fall into this sample, thus the need for additional enrolment. Additionally, it is expected that 10% of those randomised will drop-out before the end of the study.

The number of patients required to enrol will be reviewed and updated by the Trial Steering Committee (TSC) as new recruitment information accumulates. This will not change the goal of 224 patients completing the study who had mild OSA per the AASM 2012 guidelines.

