5.7 Primary Endpoint Analysis

The primary endpoint measure is the change in the Energy and Vitality subscale of the SF-36 questionnaire from baseline (i.e., pre-treatment) to 3 months post-randomization. It is a continuous variable.

The primary endpoint will be analysed using a mixed-effects repeated measures model to account for missing values. The model will be set up as follows: The Energy and Vitality subscale is the dependent variable, visit (baseline and month 3) is the repeated measure (a fixed effect), subject and site are random effects (with subject nested in site) and treatment group by visit is a fixed effect. In the case that the primary endpoint was not homogeneous across study sites (as discussed in Section 5.3), a treatment by visit by site interaction will also be included in the primary endpoint model as a random effect. Results will be presented as the mean difference in the change score from baseline to 3 months (adjusted for baseline score, as appropriate) between the two treatment groups with a 95% confidence interval at 3 months and p-value for the treatment group effect.

As a sensitivity analysis of the primary endpoint, a similar mixed-effects repeated measures model to the above will be constructed, that also adjusts for other baseline and demographic variables that were found to be imbalanced between treatment groups per Section 5.6. The mean difference in change score from baseline to 3 months will be presented with a 95% confidence interval at 3 months.

For these analyses of the primary endpoint, a P-value of less than 0.05 will be used to indicate statistical significance. Analyses of the primary endpoint will be generated for the ITT-1 population.

A second sensitivity analysis for the primary endpoint will be generated using the CC-1 population.

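### If the site-interaction test triggers, SAP 5.3 and 5.7 add different random effects to the primary model, and the 5.3 term cannot carry site variation in the change score

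*SAP*

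**What the plan says.** SAP 5.3 (Data Pooling) first fits a model with the change from baseline to 3 months as the outcome and tests the site-by-treatment interaction at 0.10. If the treatment effect is judged to differ between sites, "then study site and treatment*site will be" "included as random effects in the mixed-effects repeated measures model for the primary endpoint analysis".

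SAP 5.7 (Primary Endpoint Analysis) defines that repeated measures model. The outcome is the Energy and Vitality score itself at baseline and month 3, not the change. Visit and treatment by visit are fixed effects. Site, and subject within site, are random from the start. For the same trigger, with a cross-reference to 5.3, "a treatment by visit by site interaction will also be included in the primary endpoint model as a random effect". The reported result is the difference between arms in change from baseline to 3 months, with a 95% CI and a p-value judged at 0.05.

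The amendment in SAP section 8 says that the primary analysis was carried out as specified. It does not say whether the trigger was met or which site term was used.

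**The concern.** One trigger leads to two different random-effects structures for the one confirmatory analysis, and they are not interchangeable. In the change-score model used for the test, `treatment*site` does mean that the effect on change varies by site. SAP 5.3 then carries the same label into a model for the score at each visit, where it means something else: a site-specific gap between arms that is already present at baseline and stays constant. Only a term that includes visit can represent a CPAP effect on change that varies by site.

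At stake are the primary confidence interval and p-value. Someone who followed 5.3 alone would believe that heterogeneity had been allowed for when it had not. The second statistician, whom SAP section 6 asks to confirm that the SAP was followed, would find two models that both match the text.

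**Working it through.** **Inputs from the documents**
- 112 per arm: "The sample size of 224 (112 per arm) is based on statistics observed in the MOSAIC study".
- Change-score SDs of 17.0 (CPAP) and 18.1 (control): "with a mean change of 4.2 (SD 18.1) in the Control group and 10.8 (SD 17.0) in the CPAP Treatment group".
- Target difference 6.6 points; two-sided 5%, 80% power; 1:1 allocation (SAP 4.2 and 4.6).
- 11 participating centres (SAP 4.2).

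**Assumptions not in the documents**
- tau, the SD between sites of the true treatment effect on change: 0 to 5 points, with 6.6 as an extreme.
- Equal site sizes in the closed form.
- For the model fits: SD of the score at one visit 20, site variance 10, equal residual variance at both visits.

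**1. The plan's own figure.** The sum of squared SDs is 17.0² + 18.1² = 616.61. Then n per arm = (1.960 + 0.842)² × 616.61 / 6.6² = 111.1, rounded up to 112, or 224 in total, with power 80.3%. The stated size reproduces.

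**2. Why the 5.3 term cancels.** For a subject in site j and arm k at visit v, write

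score = fixed part(k, v) + site(j) + subject + b(j, k) + c(j, k, v) + error,

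where b is the 5.3 term and c is the 5.7 term. In month 3 minus baseline, b(j, k) − b(j, k) = 0, while c(j, k, month 3) − c(j, k, baseline) remains. The difference between arms in change at site j therefore contains four c terms and no b term. If the c terms are independent with variance V, then tau² = 4V. Site also cancels and is already random in 5.7, so listing study site in 5.3 adds nothing.

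**3. Numerical check of the cancellation.** The generalised least squares standard error of the treatment-by-visit contrast was computed with 5.3 variances of 10, 40 and 100.
- Complete data: 2.346 with or without the term, for equal and unequal sites.
- 10% of month-3 scores missing, equal sites: 2.4696 without the term and at most 2.4714 with it (under 0.1%).
- Common baseline mean imposed on both arms: 2.108 without the term and 2.232 with it at variance 40. The term then enters in part, but it still describes a gap that is constant over visits.

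**4. Size.** SE without heterogeneity = √(616.61 / 112) = 2.346. SE with heterogeneity = √(616.61 / 112 + tau² / 11). If it is ignored, type I error = 2Φ(−1.96 × 2.346 / SE).

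| tau | tau²/11 | SE, 5.3 term | SE, 5.7 term | Ratio | Type I error if ignored |
|---|---|---|---|---|---|
| 0 | 0 | 2.346 | 2.346 | 1.00 | 5.0% |
| 2 | 0.364 | 2.346 | 2.423 | 1.03 | 5.8% |
| 3 | 0.818 | 2.346 | 2.515 | 1.07 | 6.7% |
| 5 | 2.273 | 2.346 | 2.789 | 1.19 | 9.9% |
| 6.6 | 3.960 | 2.346 | 3.077 | 1.31 | 13.5% |

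**5. Fitted models.** REML fits to 300 simulated trials per setting (11 sites, 10 per arm per site) agree on the mechanism. The 5.3 standard error never differed from that of the model with no interaction term by more than 0.0014. Mean standard errors under 5.3 and 5.7 were 2.39 and 2.59 at tau 3.3, and 2.40 and 2.81 at tau 5. Coverage under 5.3 was 96% at tau 0, 94% at tau 3.3 and 86% at tau 5, with a simulation error of 1 to 2 points. In the tau 5 batch the estimates varied more than theory predicts (empirical SD 3.07, against √(616.61 / 110 + 25 / 11) = 2.81), so the closed-form 90% is the safer figure there. The 0.10 test triggered in 18% of trials at tau 3.3 and 34% at tau 5.

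**The case against.** The strongest reply is that the right term is already in the SAP. Section 5.7 defines the primary model, points back to 5.3 for the trigger and names treatment by visit by site. The 5.3 wording can be read as shorthand carried over from the change-score model. Nothing in 5.3 forbids the 5.7 term, and a model with both would carry the heterogeneity. This stands to a large extent: harm needs the 0.10 test to be significant, sites truly to differ, and an analyst to fit the 5.3 terms without the 5.7 term. The shorthand reading is weakened because 5.3 names the repeated measures model explicitly, and `treatment*site` is a legitimate random term there, so software would fit it without complaint.

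A reader might go further and infer that the planned primary confidence interval is too narrow, or that the reported one was. The documents do not support that. They do not show that the trigger was met, and 5.7 as written avoids the problem. Undercoverage also presumes inference to a wider population of sites, which a random site effect implies but the SAP does not spell out.

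It is also fair to say that tau is unknown and that 5 points is large against a 6.6-point effect. At tau 2 the interval differs by only 3%.

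**Conclusion.** The inconsistency is real and sits in the rule for the primary analysis, but it is conditional. If the trigger is met and only the 5.3 terms are fitted, the primary interval omits the site variation that led to the step; fitting the 5.7 term avoids this. The cancellation is exact with complete data, almost exact with 10% of month-3 scores missing, and partial if a common baseline mean is imposed. Even then the 5.3 term does not model variation in the change.

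Over assumed tau of 2 to 5 points, the 5.7 interval is about 3% to 19% wider, and ignoring the heterogeneity raises type I error from 5% to about 6% to 10%. These figures rest on 11 equal sites, 112 per arm, the SAP's planning SDs and normal limits. SAP 4.8 says that the SF-36 scores will be norm-based, so tau is best read relative to the 6.6-point planning effect: about 0.3 to 0.8 of it (2 / 6.6 and 5 / 6.6).

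**What to change.** In SAP 5.3, replace study site and `treatment*site` with treatment by visit by site, so that 5.3 and 5.7 name the same term. Study site can be dropped from that sentence because 5.7 already makes it random. In the trial report, state whether the 0.10 test was significant and which site term, if any, was in the primary model.

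It would help to name the degrees-of-freedom method in the same edit. With about 11 sites, normal limits can be slightly short even with the 5.7 term: in the tau 5 simulations coverage was 91% with normal limits and 95% with t on 10 degrees of freedom, although that batch was more variable than expected.

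The cost is one phrase in the SAP and one sentence in the report. The downside is a wider primary confidence interval if the trigger is met.

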5.4 Missing Data

The number and percentage of patients with missing data for each outcome measure at each time point will be reported by treatment group. A completed outcome measure refers to a completed questionnaire with a non-missing summary score. Questionnaires where too many questions were left blank, hindering the calculation of one or more summary scores, will be counted as a missing outcome measure for the corresponding endpoint.

The primary analysis uses a mixed-effects repeated measures model, which assumes data is missing at random (MAR) and incorporates all available information from all subjects.

Baseline characteristics will be summarised for those who did and did not complete the SF-36 energy and vitality questions at the 3-month follow-up visit, by treatment group, to describe any characteristics related to missingness that can be observed.

5.5 Patient Accountability

A CONSORT flowchart will be constructed to summarise the progression of patients through each study stage for each study population, and reasons for drop-out or exclusions at each stage. The flowchart will show the number of patients in each treatment group who (1) met the initial study criteria, (2) were randomly assigned, (3) received intended treatment, (4) completed specified visits, and (5) were analysed for the primary endpoint. The flowchart will present results overall and for each study population (mild OSA per AASM 2012, mild OSA per AASM 2007 and moderate/severe OSA per AASM 2012).

Protocol deviations from will be presented descriptively by treatment group with the number and percent of total deviations for each deviation type. Protocol deviations include:

Missed 3-month visit

Out of window 3-month visit (visit window defined as 90 days + 1 week)

Incomplete or missing SF-36 Energy and Vitality question responses

The numbers (with percentages) of patients completing the study and lost to follow-up (defaulters and withdrawals) over the 3-month period of the study will be presented by treatment group. Additionally, reasons for losses will be summarized.

5.6 Comparability Analysis of Baseline Characteristics

Patients in the two treatment groups will be compared with respect to baseline and demographic characteristics (e.g., ethnicity, medical history), minimisation factors for randomisation (i.e., gender, age, BMI), and baseline quality of life endpoints for the ITT-1 population.

Baseline sleep test parameters will be compared by treatment group for the ITT-1 and ITT-2 populations.

Descriptive statistics within each treatment group will be presented for demographic and baseline values. For binary and categorical variables, the number evaluated, counts (with percentages) and 95% exact confidence limits for the percentage will be presented. For continuous variables, the number evaluated, mean, standard deviation, median, minimum, maximum, and 95% confidence interval for the mean will be presented. Treatment groups will be compared with respect to baseline variables in order to test that the groups are balanced. For continuous variables, a student's t-test or Wilcoxon rank sum test will be used, as appropriate. For categorical and binary endpoints, Fisher's exact test will be utilized. All tests will be tested using a Type I error rate of 0.05.

